## **8.5. Diet/Activity/Other Considerations**

### **8.2.9 Diet**

Subjects should maintain a normal diet unless modifications are required to manage an adverse event such as diarrhea, nausea, or vomiting.

### **8.2.10 Contraception**

Pembrolizumab may have adverse effects on a fetus in utero. Furthermore, it is not known if pembrolizumab has transient adverse effects on the composition of sperm.

For this trial, male subjects will be considered to be of non-reproductive potential if they have azoospermia (whether due to having had a vasectomy or due to an underlying medical condition).

Female subjects will be considered of non-reproductive potential if they are either:

- (1) postmenopausal (defined as at least 12 months with no menses without an alternative medical cause; in women  $\geq 45$  years of age a high follicle-stimulating hormone [FSH] level in the postmenopausal range may be used to confirm a post-menopausal state in women not using hormonal contraception or hormonal replacement therapy. In the absence of 12 months of amenorrhea, at least two FSH measurements should be obtained);
  - OR
  - OR
- (2) have had a hysterectomy and/or bilateral oophorectomy, bilateral salpingectomy, or bilateral tubal ligation/occlusion at least 6 weeks prior to screening;
- (3) has a congenital or acquired condition that prevents childbearing.

Female and male subjects of reproductive potential must agree to avoid becoming pregnant or impregnating a partner, respectively, while receiving pembrolizumab and for 120 days after the last dose. Subjects must comply with one of the following:

- (1) practice abstinence\* from heterosexual activity;
- OR

(2) use (or have their partner use) acceptable contraception during heterosexual activity.

Acceptable methods of contraception are\*\*:

- Single method (one of the following is acceptable):
  - intrauterine device (IUD)
  - vasectomy of a female subject's sole male partner
  - contraceptive rod implanted into the skin
- Combination method (requires use of two of the following):
  - diaphragm with spermicide (cannot be used in conjunction with cervical cap/spermicide)
  - cervical cap with spermicide (nulliparous women only)
  - contraceptive sponge (nulliparous women only)
  - male condom or female condom (cannot be used together)
  - hormonal contraceptive: oral contraceptive pill (estrogen/progestin pill or progestin- only pill), contraceptive skin patch, vaginal contraceptive ring, or subcutaneous contraceptive injection

\*Abstinence (relative to heterosexual activity) can be used as the sole method of contraception if it is consistently employed as the subject's preferred and usual lifestyle and if considered acceptable by local regulatory agencies and ERCs/IRBs. Periodic abstinence (e.g. calendar, ovulation, sympto-thermal, post-ovulation methods, etc.) and withdrawal are not acceptable methods of contraception.

\*\*If a contraceptive method listed above is restricted by local regulations/guidelines, then it does not qualify as an acceptable method of contraception for subjects participating at sites in this country/region.

Subjects should be informed that taking the study medication may involve unknown risks to the fetus (unborn baby) if pregnancy were to occur during the study. In order to participate in the study, subjects of childbearing potential must adhere to the contraception requirement (described above) from the day of study medication initiation (or 14 days prior to the initiation of trial treatment [Cycle 1 Day 1] for oral contraception) throughout the study period up to 120 days after the last dose of trial therapy. If there is any question that a subject of childbearing potential will not reliably comply with the requirements for contraception, that subject should not be entered into the study.

### **8.2.11 Use in Pregnancy**

If a subject inadvertently becomes pregnant while on treatment with pembrolizumab, the subject will immediately be removed from the study. The site will contact the subject at least monthly and document the subject's status until the pregnancy has been completed or terminated. The outcome of the pregnancy will be reported to the Sponsor-Investigator and to Merck without delay and within 24 hours to the Sponsor-Investigator and within 2 working days to Merck if the outcome is a serious adverse experience (e.g., death, abortion, congenital

anomaly, or other disabling or life-threatening complication to the mother or newborn).

The study investigator will make every effort to obtain permission to follow the outcome of the pregnancy and report the condition of the fetus or newborn to the Sponsor. If a male subject impregnates his female partner the study personnel at the site must be informed immediately and the pregnancy reported to the Sponsor-Investigator.

#### **8.2.12 Use in Nursing**

It is unknown whether pembrolizumab is excreted in human milk. Since many drugs are excreted in human milk, and because of the potential for serious adverse reactions in the nursing infant, subjects who are breast-feeding are not eligible for enrollment.

### **8.6. Duration of Therapy**

In the absence of treatment delays due to adverse events, treatment may continue for up to 2 years (35 cycles of pembrolizumab) or until one of the following criteria applies:

- Disease progression
- Intercurrent illness that prevents further administration of treatment
- Unacceptable adverse events(s)
- Patient decides to withdraw from the study
- General or specific changes in the patient's condition render the patient unacceptable for further treatment in the judgment of the investigator

### **8.7. Duration of Follow Up**

Patients will be followed for 4 weeks after completion or removal from study or until death, whichever occurs first. Patients removed from study for unacceptable adverse events will be followed until resolution or stabilization of the adverse event..

### **8.8. Criteria for Removal from Study**

Patients will be removed from study when any of the criteria listed in [Section 6.5.1](#) applies. The reason for study removal and the date the patient was removed will be documented in the Case Report Form.

## **9. DOSING DELAYS/DOSE MODIFICATIONS**

### **9.1. Dose Modification for Pembrolizumab**

Adverse events (both non-serious and serious) associated with pembrolizumab exposure may represent an immunologic etiology. These adverse events may occur shortly after the first dose or several months after the last dose of treatment. Pembrolizumab must be withheld for drug- related toxicities and

severe or life-threatening AEs as per Table 5 below. See [Section 8.3.6](#) for supportive care guidelines, including use of corticosteroids.

**Table 5 Dose Modification Guidelines for Pembrolizumab-Related Adverse Events**

Toxicity	Hold Treatment For Grade	Timing for Restarting Treatment	Treatment Discontinuation
Diarrhea/Colitis	2-3	Toxicity resolves to Grade 0-1	Toxicity does not resolve within 12 weeks of last dose or inability to reduce corticosteroid to 10 mg or less of prednisone or equivalent per day within 12 weeks
	4	Permanently discontinue	Permanently discontinue
	2	Toxicity resolves to Grade 0-1	Toxicity does not resolve within 12 weeks of last dose
AST, ALT, or Increased Bilirubin	3-4	Permanently discontinue (see exception below) a	Permanently discontinue
Toxicity	Hold Treatment For Grade	Timing for Restarting Treatment	Treatment Discontinuation
Type 1 diabetes mellitus (if new onset) or Hyperglycemia	T1DM or 3-4	Hold pembrolizumab for new onset Type 1 diabetes mellitus or Grade 3-4 hyperglycemia associated with evidence of beta cell failure	Resume pembrolizumab when patients are clinically and metabolically stable
Hypophysitis	2-4	Toxicity resolves to Grade 0-1. Therapy with pembrolizumab can be continued while endocrine replacement therapy is instituted	Toxicity does not resolve within 12 weeks of last dose or inability to reduce corticosteroid to 10 mg or less of prednisone or equivalent per day within 12 weeks
Hyperthyroidism	3	Toxicity resolves to Grade 0-1	Toxicity does not resolve within 12 weeks of last dose or inability to reduce corticosteroid to 10 mg or less of prednisone or equivalent per day within 12 weeks
	4	Permanently discontinue	Permanently discontinue
Hypothyroidism		Therapy with pembrolizumab can be continued while thyroid replacement therapy is instituted	Therapy with pembrolizumab can be continued while thyroid replacement therapy is instituted
Infusion Reaction	2 b	Toxicity resolves to Grade 0-1	Permanently discontinue if toxicity develops despite adequate premedication
	3-4	Permanently discontinue	Permanently discontinue
Pneumonitis c	2	Toxicity resolves to Grade 0-1	Toxicity does not resolve within 12 weeks of last dose or inability to reduce corticosteroid to 10 mg or less of prednisone or equivalent per day within 12 weeks
	3-4	Permanently discontinue	Permanently discontinue
Renal Failure or Nephritis	2	Toxicity resolves to Grade 0-1	Toxicity does not resolve within 12 weeks of last dose or inability to reduce corticosteroid to 10 mg or less of prednisone or equivalent per day within 12 weeks
	3-4	Permanently discontinue	Permanently discontinue
All Other Drug-Related Toxicity d	3 or Severe	Toxicity resolves to Grade 0-1	Toxicity does not resolve within 12 weeks of last dose or inability to reduce corticosteroid to 10 mg or less of prednisone or equivalent per day within 12 weeks
	4	Permanently discontinue	Permanently discontinue

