### **8.2.2 Dose Modification (Escalation/Titration/Other)**

The Common Terminology Criteria for Adverse Events version 4.0 (CTCAE 4.0) must be used to grade the severity of adverse events.

If appropriate, the investigators may attribute each toxicity event to either one of the investigational agents and use stepwise dose modifications according to Table 5. Pembrolizumab dose reductions are not permitted. Pembrolizumab treatment may be interrupted or discontinued due to toxicity.

If a dose level reduction for toxicity occurs with azacitidine, the dose may not be re-escalated. Dose modifications are always based on the previous cycle.

Subjects may have up to 1 dose level reductions of azacitidine as described in Table 6. If further toxicity occurs or the criteria for resuming treatment are not met, the subject must be discontinued from treatment.

If a toxicity is not otherwise specified, investigators should refer to the label or local standard of care for dose adjustments. At the investigator's discretion, dose modification according to Table 5 is allowed for intolerable Grade 2-3 toxicities that are not specified in the tables below.

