#### **8.2.8      Supportive Care Guidelines**

Subjects should receive appropriate supportive care measures as deemed necessary by the treating investigator. Suggested supportive care measures for the management of adverse events with potential immunologic etiology are outlined below. Toxicities associated or possibly associated with pembrolizumab should be managed according to standard medical practice. Additional tests, such as autoimmune serology or biopsies, should be used to evaluate for a possible immunogenic etiology. Attempts should be made to rule out other causes such as metastatic disease or bacterial or viral infection, which might require additional supportive care.

Although most immune-related adverse events observed with immunomodulatory agents have been mild and self-limiting, such events should be recognized early and treated promptly to avoid potential major complications. Discontinuation of pembrolizumab may not have an immediate therapeutic effect, and in severe cases, immune-related toxicities may require acute management with topical steroids, systemic corticosteroids, or other immunosuppressive agents. The treatment guidelines are intended to be applied when the investigator determines the events to be related to trial treatment.

Note: if after the evaluation the event is determined not to be related, the investigator does not need to follow the treatment guidance (as outlined below).

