**Note: Permanently discontinue for any severe or Grade 3 drug-related AE that recurs or any life-threatening event.**

a For patients with liver metastasis who begin treatment with Grade 2 AST or ALT, if AST or ALT increases by greater than or equal to 50% relative to baseline and lasts for at least 1 week then patients should be discontinued.

b If symptoms resolve within one hour of stopping drug infusion, the infusion may be restarted at 50% of the original infusion rate (e.g., from 100 mL/hr to 50 mL/hr). Otherwise dosing will be held until symptoms resolve and the subject should be premedicated for the next scheduled dose; Refer to Table 4—Infusion Treatment Guidelines for further management details.

c For grade 2 pneumonitis, should this recur, pembrolizumab should be discontinued.

d Patients with intolerable or persistent Grade 2 drug-related AE may hold study medication at physician discretion. Permanently discontinue study drug for persistent Grade 2 adverse reactions for which treatment with study drug has been held, that do not recover to Grade 0-1 within 12 weeks of the last dose.

Dosing interruptions are permitted in the case of medical / surgical events or logistical reasons not related to study therapy (e.g., elective surgery, unrelated medical events, patient vacation, and/or holidays). Subjects should be placed back on study therapy within 3 weeks of the scheduled interruption, unless otherwise discussed with the Sponsor. The reason for interruption should be documented in the patient's study record.

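### Table 5 permits pembrolizumab to be restarted after six immune-related events for which Section 8.2.8 stops it permanently, and no text says which section governs

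*Combined protocol and SAP*

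**What the plan says.** Two parts of the protocol tell the investigator what to do with pembrolizumab after an immune-related event.

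**Section 8.2.8 (Supportive Care Guidelines)** goes event by event. It permanently stops pembrolizumab for Grade 3 or 4 ocular events, myocarditis and neuropathy. It does the same for myasthenia gravis and Guillain-Barre syndrome at any grade, and for meningoencephalitis at all grades. On its own standing it says two things: "Suggested supportive care measures for the management of adverse events with potential immunologic etiology are outlined below", and "The treatment guidelines are intended to be applied when the investigator determines the events to be related to trial treatment".

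**Section 9.1 with Table 5** makes withholding for drug-related toxicity mandatory as the table sets out. The table has no row for any of the six events, so the last row, "All Other Drug-Related Toxicity", applies. At Grade 3 or severe, that row holds the drug and permits restart at Grade 0-1; at Grade 4 it stops for good. The note below the table adds: "Permanently discontinue for any severe or Grade 3 drug-related AE that recurs or any life-threatening event". Footnote d covers Grade 2: "Patients with intolerable or persistent Grade 2 drug-related AE may hold study medication at physician discretion".

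**Section 8.2.2** gives two further routes. One is discretionary: "dose modification according to Table 5 is allowed for intolerable Grade 2-3 toxicities that are not specified in the tables below". The other reads: "If a toxicity is not otherwise specified, investigators should refer to the label or local standard of care for dose adjustments". Neither mentions the guidelines in 8.2.8.

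**The concern.** The dose-modification table is what an investigator consults when deciding whether to give the next infusion. For these six events it is less strict than the event-specific text elsewhere in the same protocol. A subject with a first Grade 3 myocarditis that resolves, or with Guillain-Barre syndrome or meningoencephalitis below Grade 4, could be re-treated with Table 5 cited as authority, although 8.2.8 ends treatment. Two subjects with the same event could also be managed differently, with no text to show which decision was correct.

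**Working it through.** No formula applies; this is a comparison of text. Table 5 and the 8.2.8 guidelines both address treatment-related events, so they cover the same cases.

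| Event | Grade | Section 8.2.8 | Table 5, note and footnote d | Differ? |
|---|---|---|---|---|
| Ocular, myocarditis, neuropathy | First 3 | Permanent stop | Hold; restart permitted at Grade 0-1 | Yes |
| Same three | 4 | Permanent stop | Permanent stop | No |
| Myasthenia gravis, Guillain-Barre, meningoencephalitis | 1 | Permanent stop | No action listed | Yes |
| Same three | 2 | Permanent stop | Optional hold | Yes |
| Same three | First 3 | Permanent stop | Hold; restart permitted at Grade 0-1 | Yes |
| Same three | 4 | Permanent stop | Permanent stop | No |

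Event types affected: 3 (at a first Grade 3) + 3 (at Grades 1-3) = 6.

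**When Table 5 would still force a stop.** It does so after a Grade 3 or severe event if the toxicity has not resolved within 12 weeks, if steroids cannot be brought down to the stated dose within 12 weeks, if the event recurs, or if it is life-threatening. A held, persistent Grade 2 event that does not recover within 12 weeks also leads to a stop. None of these rules reaches a first Grade 3 event that resolves in time.

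**Search for a precedence rule.**
- Section 9.1: the mandatory verb attaches to withholding as per Table 5. The supportive care section is then cited for supportive care and corticosteroid use. The two are not ranked.
- Section 8.2.8: described both as suggested and as intended to be applied. The two descriptions pull in opposite directions.
- Section 8.2.2: one sentence covers toxicities missing from the tables and the other covers toxicities specified nowhere. Neither settles a difference between two rules that are both specified.

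**Link to the DLT definition.** Section 5.2 counts as a DLT any toxicity managed by stopping pembrolizumab, and it cites 9.1. Drug-related Grade 3 non-hematological events are already DLTs, so the choice of section matters only at Grades 1-2. A drug-related Grade 1-2 myasthenia gravis, Guillain-Barre or meningoencephalitis event in the 6-subject cohort is a DLT if 8.2.8 is followed, but need not be if Table 5 is followed. Under Section 1.1, two subjects with DLTs out of six stop accrual at that dose level.

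**The case against.** The best defence is that this is a gap in a table and not a contradiction. The last row of Table 5 is residual, and its column gives the timing for a restart. It does not require one. Stopping for good under 8.2.8 also satisfies Table 5, so both can be obeyed. Section 8.2.2 lets pembrolizumab be discontinued for toxicity, and Section 6.5.1 requires discontinuation for unacceptable adverse experiences. The natural reading is that event-specific text beats a residual row.

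Much of this stands. A reader might infer that Table 5 obliges re-treatment, or that the sections clash at every grade; the text supports neither. But no sentence says that the specific rule wins, and that principle would not settle the protocol's other differences. For Grade 2 pneumonitis both sections are specific and still disagree: 8.2.8 lets the hold run past 12 weeks for a steroid taper, while Table 5 discontinues. Calling the 8.2.8 measures suggested also gives an investigator grounds to treat them as advice.

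Two stronger readings should be set aside.

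- **That one sentence giving precedence to the stricter rule is needed.** Other differences do exist: Grade 4 adrenal insufficiency, amylase/lipase elevation, hyperthyroidism and hypophysitis; symptomatic hypothyroidism; the steroid-taper limit; and recurrent Grade 2 events. On the last, footnote c says "For grade 2 pneumonitis, should this recur, pembrolizumab should be discontinued", where 8.2.8 has no recurrence rule. But a blanket sentence would override event-specific rules. It would force a permanent stop for Grade 4 amylase/lipase elevation or adrenal insufficiency, where 8.2.8 withholds and resumes, although Table 1 admits some subjects with raised amylase or lipase. It would also require withholding for symptomatic hypothyroidism, where Table 5 continues treatment. Those are clinical trade-offs.
- **That the references to 8.3.6 in Sections 9.1 and 10.2 point nowhere.** Section 8.3 has six subsections misnumbered 8.2.3 to 8.2.8, and Supportive Care Guidelines is the sixth. The reference is right and the heading is wrong. Contraception shows the same fault: it is cited as 8.5.2 but headed 8.2.10 under 8.5.

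**Conclusion.** The point holds for six event types. For ocular events, myocarditis and neuropathy at a first Grade 3, and for myasthenia gravis, Guillain-Barre syndrome and meningoencephalitis at Grades 1-3, Section 8.2.8 ends pembrolizumab and Table 5 does not. No text says which governs.

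This should be corrected because the operative table permits re-treatment that the protocol rules out elsewhere, after events that include myocarditis and Guillain-Barre syndrome. It is a drafting fault with a safety consequence and leaves the primary PFS analysis unaffected. Its expected frequency among the 31 to 37 planned subjects cannot be given, because the documents state no rates for these events. The conclusion assumes only that the event is judged treatment-related, which both sections require.

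**What to change.** 1. Add rows to Table 5 that permanently stop pembrolizumab for Grade 3-4 ocular events, myocarditis and neuropathy, and for myasthenia gravis, Guillain-Barre syndrome and meningoencephalitis at any grade.
2. In Section 8.2.2, cite the supportive care guidelines next to Table 5.
3. Do not add a general stricter-rule sentence. The investigators should settle the other differences event by event.
4. Leave the 8.3.6 references alone; the subheadings under 8.3 are what need renumbering.

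The cost is a wording amendment, with no change to sample size, analysis or the text of Section 5.2. There is one downside to declare. Once the rows are in 9.1, a drug-related Grade 1-2 myasthenia gravis, Guillain-Barre or meningoencephalitis event in the 6-subject cohort counts as a DLT through the 5.2 bullet that cites 9.1. It would already count if 8.2.8 were followed, so the amendment removes the ambiguity and does not add a new criterion.

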**Note: Permanently discontinue for any severe or Grade 3 drug-related AE that recurs or any life-threatening event.**

a For patients with liver metastasis who begin treatment with Grade 2 AST or ALT, if AST or ALT increases by greater than or equal to 50% relative to baseline and lasts for at least 1 week then patients should be discontinued.

b If symptoms resolve within one hour of stopping drug infusion, the infusion may be restarted at 50% of the original infusion rate (e.g., from 100 mL/hr to 50 mL/hr). Otherwise dosing will be held until symptoms resolve and the subject should be premedicated for the next scheduled dose; Refer to Table 4—Infusion Treatment Guidelines for further management details.

c For grade 2 pneumonitis, should this recur, pembrolizumab should be discontinued.

d Patients with intolerable or persistent Grade 2 drug-related AE may hold study medication at physician discretion. Permanently discontinue study drug for persistent Grade 2 adverse reactions for which treatment with study drug has been held, that do not recover to Grade 0-1 within 12 weeks of the last dose.

Dosing interruptions are permitted in the case of medical / surgical events or logistical reasons not related to study therapy (e.g., elective surgery, unrelated medical events, patient vacation, and/or holidays). Subjects should be placed back on study therapy within 3 weeks of the scheduled interruption, unless otherwise discussed with the Sponsor. The reason for interruption should be documented in the patient's study record.

